4.2 Exclusion Criteria

Potential participants meeting any of the exclusion criteria at baseline will be excluded from participating in any part of the study. The exclusion criteria for this study include:

1. Not a registered Blued app user
2. < 18 years of age
3. Not male sex at birth
4. Does not report anal sex with a man in the last 6 months
5. Has previously tested positive for HIV
6. Not eligible for PrEP per published China guidance
7. Unable to complete study instruments in Mandarin Chinese
8. Not a resident of the metropolitan area of Beijing or Chengdu, China
9. Currently enrolled in another HIV prevention study
10. Evidence of fraudulent participation, such as a duplicate IP address, multiple screening attempts, duplicate emails, etc.

4.3 Recruitment

Participants will be recruited using banner advertising and inbox messages delivered through the Blued app. We will target men at least 18 years old who live in the metropolitan area of one of the two cities where the study is being conducted. When interested men click on a banner advertisement, they will be taken to a landing page containing basic study information that includes a short description of study activities. If they click on a button to advance, they will be directed to a short eligibility screener to determine whether they meet the eligibility criteria. Men who do not meet the eligibility criteria will be taken to a screen thanking them for their interest in the study. Men who do screen preliminarily eligible will be asked to provide their contact information, including an email address, a cell phone number that can receive text messages, and a name or nickname so study staff can contact them. No identifying information will be collected from participants determined to be ineligible at screening.

5.0 PILOT STUDY PROCEDURES

Baseline procedures are identical for all study participants. These procedures include rescreening for eligibility, fraud deterrence, informed consent, and a baseline survey.

5.1 Enrollment Procedures

5.1.1 Fraud Detection and Eligibility Confirmation

To mitigate fraudulent participation, a list of Blued user accounts eligible for study participation will be developed prior to the launch of the pilot study. Accounts that are created after study initiation will not be eligible for the study. This will prevent attempts to create fraudulent additional accounts for rescreening or to collect multiple incentives.

5.1.2 Informed Consent and Enrollment

Because men will not be consented and enrolled at an “in-person” visit, the consent process will be administered via the Blued app. Participants who are eligible based on screening and fraud checks will be provided an electronic study consent on a secure electronic survey platform and will be able to download and save a copy as well. Participants will be able to contact study staff should they have any questions during this process. The consent form describes all study procedures, including confidentiality and privacy, information about potential risks, discomforts, benefits of participation, and information regarding who they can contact with further questions. It also states that participation is voluntary, that participants may decide not to take part or to withdraw from the study at any time without penalty or loss of any benefit to which they might otherwise be entitled, and that study participation is in no way related to being able to access or continue getting care or services. Participants can refuse to answer any questions, and can withdraw from the study at any time.

A brief quiz will be developed to verify understanding of key elements of the consent form. After reviewing the consent form, potential participants will be forwarded to the consent quiz. Those who do not receive a sufficient score on the quiz will be directed back to the consent form for further review before completing the quiz.

Upon successful completion of the consent quiz, potential participants will provide consent using an electronic method to document signature on the electronic consent form. Informed consent must be obtained before any study procedures are performed. The consent form will be available in Mandarin Chinese.

Upon signing of the consent form, participants will notify participants to complete the baseline survey through Blued’s secure, encrypted survey platform.

5.2 Standard of Care

Assessed during the baseline study period, participants will have access to the existing Blued app and local health services. Blued app access currently includes health education components such as information regarding HIV testing and pre-recorded health messages from Chinese celebrities. Participants will have access to in-person, no cost services for HIV testing and condom pick-up from local NGOs that support MSM in both pilot cities.

5.3 Intervention Description

During the intervention period, study participants will receive the enhanced version of the Blued app with Blued+ service. Blued+ serves as the primary participant-facing component of the intervention.

5.3.1 Blued+ Service Core Components

All Blued+ intervention participants will have a health portal that houses all HIV prevention functionalities. In the portal, users will be able to explore health-supporting functions of Blued+ and access offline services such as ordering of prevention kits and supplies.

Behavioral Risk Assessment

Blued+ will use an engaging “health quiz” function that will serve to screen participants into appropriate services and to provide information relevant to the degree of protection based on current self-reported behaviors. Screening will allow users to access services most relevant to them, such as home HIV testing for users who have not recently tested or condom “choice” packages with different types of condoms for users dissatisfied with their current condoms. Information relevant to the current degree of protection will be provided through a risk dashboard. This function will inform those who receive risk screening, as well as provide clear mechanisms for individuals to mitigate their risk by accessing prevention services.

HIV Testing

Participants will have easy access in Blued+ to either order an in-home HIV test or schedule an HIV test appointment with their local provider. For the in-home option, participants will be mailed a HIV in-home test. Orders will be manually filled by study staff and mailed using the Chinese postal system. Participants preferring an in-person test will be able to select from local HIV test providers and schedule a test with that provider through an electronic calendaring system. Participants unsure of their preferred testing mode will be able to access information regarding the types of HIV testing available and their relevant benefits (e.g. in-home is saliva-based, no blood draw) and limitations (e.g. in-home has lower sensitivity for detecting HIV).

Linkage to Care for those Testing HIV Positive

Linkage to care will be available for those using home testing modalities. Those ordering home tests will be notified by Blued+ and through mailed materials accompanying the test kit that counseling and treatment are available. Brief surveys will also be sent to those ordering home test kits to query results and to refer to linkage to care services as appropriate. Experienced counselors at local HIV prevention organizations will provide linkage services through phone calls or in-person services.

In-App Screening and Referral to PrEP and STI Services

Both the baseline survey and periodic health quizzes will assess behavioral PrEP indication and STI testing frequency. Participants indicated for PrEP or STI testing will be able to schedule an appointment for PrEP or STI evaluation. For those interested in PrEP, the appointment will be in-person at a study clinic, or online with the Blued licensed PrEP clinician; those only interested in STI services will be scheduled for laboratory testing at their local NGO. Participants will also be able to access information modules describing PrEP and STIs within Blued+. A chat board or

similar communication function will allow study participants to have their questions about PrEP answered.

Provision of PrEP

Participants interested in PrEP will attend an in-person or online appointment with the study clinician at each site. The participant Blued app ID will be recorded to allow for linkage of study data and PrEP clinic visits for those who choose to access PrEP. PrEP care will follow US-CDC recommendations or Chinese recommendations if available. See the following section on PrEP with FTC/TDF for more information.

HIV Prevention Platform

An electronic platform will help participants formulate HIV prevention strategies, and monitor progress towards their prevention goals. This will allow men to create plans for HIV testing, condom use, and PrEP. The platform will feature commodity ordering offerings that provide notifications. Those who have initiated PrEP care may receive reminders regarding medication adherence and follow-up visit attendance.

5.3.2 Additional Blued+ Components

After the 3-month period, additional app components will be unlock in the health portal for each participant. These intervention components include:

Educational materials focused on PrEP as well as other sexual health topics. Topics of education may include an overview of PrEP and PrEP medication, the effectiveness of PrEP, PrEP payment, side effects, stigma, and where to access PrEP, among other topics related to prevention of HIV and STIs.

Additionally, participants will receive theory-based sexual health and prevention messages delivered via the Blued+. These messages will be developed with the goal of creating a comprehensive messaging package to improve participants' self-reported sexual health and prevention behaviors, beliefs, and attitudes. Participants will also receive a screener quiz that allows them to assess whether PrEP is right for them and encourage them and link to PrEP care. Those participants who do choose to initiate PrEP will receive the FTC/TDF, associated laboratory testing, and clinical care free of charge. Participants will be encouraged to schedule a visit with a study provider in each intervention city in-person or online, and will access PrEP free of charge through these study clinics.

5.4 PrEP

5.4.1 Additional Inclusion/Exclusion Criteria for Participants electing PrEP

In addition to the inclusion and exclusion criteria above for participants who enter the study, additional inclusion and exclusion criteria apply to participants who initiate PrEP. These criteria are based on US CDC Guidelines for PrEP or Chinese recommendations if available. All participants who choose to initiate PrEP through this study will be required to meet these guidelines, including laboratory testing.

Inclusion Criteria:

In addition to the inclusion criteria above, the inclusion criteria for PrEP are:

1. Laboratory confirmed **HIV-negative**
2. Behaviorally indicated for PrEP, including any of the following:
 - a. History of inconsistent or no condom use with more than one partner
 - b. History of inconsistent or no condom use with one partner who is not mutually monogamous
 - c. Sexual partner living with HIV who is not virally suppressed
 - d. History of a sexually transmitted infection by lab testing or self-report in the past six months
 - e. Use of post-exposure prophylaxis
 - f. Engagement in transactional sex, including sex work
 - g. Requesting PrEP
 - h. Other criteria as determined by future guidance from China
3. No contraindications to emtricitabine/tenofovir disoproxil fumarate (FTC/TDF)
4. **Creatinine clearance** of at least 60 mL/min reported by a laboratory or estimated using the Cockcroft-Gault Equation:

$$CrCL \text{ (mL/min)} = \frac{(140 - \text{age}) * \text{body weight [kg]}}{\text{Serum Cr [mg/dL]} * 72}$$

5. Willing to adhere to a PrEP dosing regimen
6. Willing to attend PrEP maintenance visits every 3 months

Exclusion Criteria

In addition to the exclusion criteria above, the exclusion criteria for PrEP are:

1. HIV-positive, either laboratory confirmed or by self-report
2. Signs or symptoms of acute HIV infection, probably recent exposure to HIV
3. **Chronic hepatitis B**
4. Creatinine clearance <60 mL/min
5. Symptoms of acute HIV infection within the prior 30 days
6. Contraindications to emtricitabine/tenofovir disoproxil fumarate (FTC/TDF)
7. Unwilling to attend PrEP maintenance visits every 3 months

5.4.2 Regimen (dose, schedule, route)

Pre-exposure prophylaxis for HIV will be available to participants through the study. Procedures will follow those set forth by the US CDC. The PrEP used in this study will be a combination of 200 mg emtricitabine (FTC) and 300 mg of tenofovir disoproxil fumarate (TDF).

5.4.3 Study Product Formulation and Preparation

FTC/TDF tablets are capsule-shaped and usually film-coated and blue. They are available in child-resistant bottles, and including a silica gel canister or sachet. Medications will be stored by partner clinics in each intervention city at appropriate temperature and discursions based on manufacturer guidance. Containers will be kept tightly closed. Product will be dispensed in accordance with manufacturer guidance. No additional preparation will be necessary.

5.4.4 Study Product Supply and Accountability

Study Product Supply and Distribution to Participants

FTC/TDF will be purchased local in China from a manufacturer with China FDA-approved FTC/TDF pills.

Once a participant has indicated interest in PrEP, he will schedule an appointment with a clinician at partner clinics in person or online at each study site. Once deemed eligible for PrEP, he will be provided enough medication for three months and given counseling to encourage adherence. The participant will be required to attend follow-up PrEP visits every three months thereafter to check adherence, creatinine as needed, and HIV status, and thus eligibility to continue PrEP. Testing for STIs will also be completed at these visits.

PrEP eligibility will be verified before any additional pills are dispensed. The serial number or other relevant tracking information of the dispensed bottles will be recorded by the study clinician or pharmacy personnel, along with a count of pills dispensed in each bottle. At each visit, participants on PrEP will be asked to return their original prescribed FTC/TDF bottles containing any remaining tablets. Remaining tablets will be counted and used along with the information on time since the last refill to calculate pill adherence.

Study Product Accountability

All pills at partner clinics will be stored at the approved site pharmacy. These pharmacies will act in accordance with Chinese guidelines around good pharmacy practice set by these National Medical Products Administration (NMPA). All study materials will be locked and secured. The site pharmacist will track all pills received from the distributor and prescribed to or returned by study participants. The pharmacist will ensure that all PrEP participants are prescribed the correct number of pills. At the end of the study period, all unused study products will be managed in accordance with local procedures.

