5.4.6 Management of Specific Toxicities on PrEP

Specific guidance related to product hold is also noted here as it pertains to the clinical management of toxicities.

- Nausea, Vomiting, and Diarrhea**

Participants with Grade 1 or 2 nausea, vomiting, or diarrhea may be treated symptomatically with hydration, oral antiemetic therapies or antiemetic suppositories at the discretion of the study investigator. The investigator should order any clinically relevant laboratory analyses per his or her judgement.

Participants with \geq Grade 3 nausea, vomiting, or diarrhea for which an alternative etiology is not established must discontinue the study drugs temporarily until Grade 2 or lower and be treated symptomatically. Should condition(s) not improve to Grade 2 or lower within seven days, the investigator should consult the PSRT for guidance on continuing the temporary discontinuation or progressing to permanent discontinuation of study drugs.

Repeat episodes of these events will be handled independently, and the instruction above will be followed for each event.

- Creatinine Clearance for PrEP**

If the creatinine clearance is <60 mL/min, study drug should be temporarily held and it should be confirmed within one week of the receipt of the results. If the calculated creatinine clearance is confirmed to be <60 mL/min, the study drug must be permanently discontinued. If re-testing yields a result ≥60 mL/min, the study investigator should consult the PSRT for further guidance on resuming study drug use, continuing the hold temporarily, or progressing to permanent discontinuation.

By which the investigator in consultation with the PSRT has determined that the case has stabilized, it may be possible to decrease the frequency of follow-up laboratory testing in addition to resumption of study drug.

- HIV Infection**

Frequent testing for HIV acquisition during the study period will allow prompt cessation of study drug in an HIV-infected participant, minimizing the risk that resistant virus will emerge. Therefore, HIV testing will be performed at PrEP start and every three months thereafter. Any enrolled participants who acquire HIV infection while on PrEP will permanently discontinue study drug but will remain in the study.

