8.1 Laboratory Specimens

As described previously, the following types of specimens will be collected for laboratory testing throughout this study for those **who initiate PrEP**:

Blood Specimen: To be used for **HIV testing**, confirmatory HIV testing, **syphilis** rapid plasma reagin (RPR), serum **creatinine**, **Hepatitis B** Surface Antigen (HBsAg), dried blood spot (DBS) for measuring tenofovir diphosphate (TVF-DP) levels in plasma for PrEP adherence measure.

Dried Blood Spot: Participants who initiate PrEP will be asked at an interim visit for permission to collect blood to create a dried blood spot (DBS) for research purposes. Participants have consented to this procedure, from the consent form, "An additional blood sample may also be collected to determine how much of the PREP drug, Truvada, is present in your blood." An additional short questionnaire, contained from currently IRB-approved survey Section B: Sexual History and Section E: PrEP Intention, will be asked for the most recent information prior to blood collection. For this additional participation, we will provide an extra 300RMB (\$45) incentive.

Urine Specimen: To be used for urethral chlamydia and gonorrhea testing

Rectal Swab Specimen: To be used for rectal chlamydia and gonorrhea testing

Pharyngeal Swab Specimen: To be used for pharyngeal chlamydia and gonorrhea testing

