11.3.2 Additional Risks for Participants on PrEP

While the purpose of this study is to design and test a mobile application for MSM in China, this study will have study clinicians prescribing PrEP in-person or remotely in accordance with FTC/TDF (emtricitabine/tenofovir disoproxil fumarate) label indication. The prescription of PrEP in the study will also follow guidance from the US Public Health Service and US Centers for Disease Control and Prevention. However, persons may have additional risks and side-effects from taking FTC/TDF.

- Antiretroviral resistance can occur if participant is HIV-infected. To minimize this risk, HIV testing will occur prior to initiation of FTC/TDF and at every follow-up PrEP visit thereafter.
- Persons may have discomfort, bruising, or a local infection at the site of venipuncture. This is a typical risk of having blood drawn in any setting. The study clinicians will have experience in phlebotomy to minimize this risk.
- Gastrointestinal side-effects, including nausea, vomiting, diarrhea, and weight loss are possible on FTC/TDF.
- The use of FTC/TDF may less commonly cause severe side effects. More serious effects may include allergic reactions (rash; itching; difficulty breathing; swelling of the face, lips, throat, or tongue); bone pain; mood changes; muscle pain or weakness; severe dizziness; symptoms of kidney problems (e.g., increased or decreased urination, increased thirst) and symptoms of liver problems (e.g., yellowing of the skin or eyes; dark urine; pale stools; persistent loss of appetite). To avoid renal toxicity, creatinine clearance levels will be assessed prior to initiation of FTC/TDF, and every three months while the participant is on FTC/TDF.
- To avoid complications with hepatitis B, participants will be screened for hepatitis B prior to initiation; those who are hepatitis B surface antigen (HBsAG) negative and hepatitis B surface antibody (HBsAB) negative will be referred for hepatitis B immunization.

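### Section 5.4.4 makes creatinine at the three-monthly PrEP visits discretionary, while 11.3.2 commits to creatinine clearance every three months; the operational section should match the safety commitment

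*Combined protocol and SAP*

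**What the plan says.** Two sections of the combined protocol and SAP address creatinine during PrEP follow-up.

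- **Section 5.4.4**, which governs supply and dispensing, requires attendance at "follow-up PrEP visits every three months thereafter to check adherence, creatinine as needed, and HIV status, and thus eligibility to continue PrEP". It adds that "PrEP eligibility will be verified before any additional pills are dispensed".
- **Section 11.3.2**, which lists the additional risks for participants on PrEP, says that to avoid renal toxicity "creatinine clearance levels will be assessed prior to initiation of FTC/TDF, and every three months while the participant is on FTC/TDF".

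Other sections bear on the point without giving a routine creatinine interval.

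- **Section 5.4.1** makes it a condition for PrEP that creatinine clearance be "of at least 60 mL/min reported by a laboratory or estimated using the Cockcroft-Gault Equation". It also requires men who start PrEP to meet the guidelines, laboratory testing included.
- **Section 5.4.6** gives the action on a low result: "If the creatinine clearance is <60 mL/min, study drug should be temporarily held". A confirmed low value means permanent discontinuation. For HIV, the same section does give a schedule: "HIV testing will be performed at PrEP start and every three months thereafter".
- **Section 8.1** says that for men who initiate PrEP "the following types of specimens will be collected for laboratory testing throughout this study", and serum creatinine is on the list.
- **Section 5.3.1** says that "PrEP care will follow US-CDC recommendations or Chinese recommendations if available". Sections 5.4.1, 5.4.2, 11.3.2 and 12.1 also refer to US guidance.

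**The concern.** In the 5.4.4 list of visit checks, creatinine alone is qualified; adherence and HIV status are not. A clinic that reads that section literally may decide at a given visit that no creatinine is needed and dispense another three months of drug. It would comply with 5.4.4 and omit a test that 11.3.2 says will be done.

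The stake is participant safety. The rule in 5.4.6 to hold the drug, confirm, and stop below 60 mL/min can act only on a measured value. The investigator's general discretion under 5.4.5 to hold the drug remains, but it does not produce a measurement. The weaker wording sits in the section that clinics will use when dispensing, and the firmer wording sits in the human-subjects section.

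**Working it through.** The plan gives no figure to reproduce here. The check is a comparison of texts, followed by a small count.

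**Step 1. Do the two wordings conflict?** Section 5.4.4 makes creatinine conditional at each three-monthly visit. Section 11.3.2 makes it unconditional at the same interval. Testing every quarter satisfies both. Testing only on judgement satisfies 5.4.4 and fails 11.3.2. So the texts can be reconciled in one direction, but 5.4.4 does not require that direction.

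**Step 2. Does other text decide it?**

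| Text | Leans towards quarterly testing? | Gives an interval? |
|---|---|---|
| 5.4.4, eligibility verified before each refill | Yes, since clearance is an eligibility criterion | No; the same paragraph describes the check as including creatinine only when needed |
| 5.4.1, at least 60 mL/min | Yes, as a criterion | No; it sets no limit on the age of the value |
| 5.4.6, creatinine paragraph | Yes, weakly; it lets laboratory follow-up become less frequent once a case has stabilized, which presupposes some frequency | No |
| 8.1, specimen list | Yes, weakly; collection runs throughout the study | No |
| 5.3.1, 5.4.1, 5.4.2, 11.3.2, 12.1, outside guidance | Unknown from the documents | None reproduced |

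The supplied text contains no schedule-of-assessments table and no statement of which section takes precedence.

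**Step 3. How many tests are at issue?**

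Inputs: 400 participants (3.2); intervention from month 3 and follow-up to month 15 (Study Design); three-month supplies (5.4.4); PrEP benchmark of 15% in 10.1 and 20% in 6.0. Assumptions: the man starts PrEP at month 3 and continues, and no study supply is given after month 15.

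- Refills fall at months 6, 9 and 12, so there are 3 checks at refills. A fourth, at month 15, arises only if a PrEP visit is held when no refill follows. No text states that such a visit takes place.
- Section 5.4.4 read alone guarantees none of these checks.
- If no repeat were ever judged necessary, the age of the starting value at the refills would be 6 − 3 = 3, 9 − 3 = 6 and 12 − 3 = 9 months. When the last supply ended, it would be 15 − 3 = 12 months.
- Men at the benchmark minimums: 0.15 × 400 = 60 and 0.20 × 400 = 80.
- Tests with 3 checks each: 3 × 60 = 180 to 3 × 80 = 240.
- Tests with 4 checks each: 4 × 60 = 240 to 4 × 80 = 320.

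Later starters would have fewer checks. The 60 and 80 are benchmark minimums, neither a forecast nor a ceiling.

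**The case against.** The best reply is that the protocol, read as a whole, already requires quarterly testing. Section 11.3.2 is mandatory and specific, while 5.4.4 has one loose phrase in a section about product supply. The eligibility check before each refill, the laboratory requirement in 5.4.1 and the specimen list in 8.1 all point the same way. Only a site that overlooks 11.3.2 would skip a test. This largely stands as an account of intent. A reader might infer that the protocol leaves the schedule wholly open, or that sites are meant to refill without renal monitoring; the documents do not support either reading. What remains is that probable intent is not an instruction, and the section used for dispensing says something weaker.

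A second reply is that the outside guidance may define when creatinine is needed. It may. But the protocol neither reproduces an interval nor says that the guidance governs that phrase, so the documents cannot confirm it.

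A third reply concerns size and cost. The oldest-value figures need a month-3 start, continuous use, no test ever judged necessary, and 11.3.2 disregarded, so they describe an extreme case. It is also fair to say that the tests are additional if 5.4.4 is the baseline, and that a shared blood draw cannot be assumed for online visits. Both points stand and are reflected in the conclusion and the cost.

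**Conclusion.** The conflict is real and should be fixed. It is a participant-safety inconsistency in wording, and quarterly testing is the likely intent. The gap is that a site following 5.4.4 as written could dispense without a current value for the 60 mL/min rule.

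On the stated assumptions, the commitment in 11.3.2 amounts to 3 checks per man at refills, or 4 with a month-15 PrEP visit. That is 180 to 240 tests, or 240 to 320, at the benchmark minimums.

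A reader might go further and infer that renal events will be missed, or try to count them. The documents give no rate of renal decline and no record of site practice, so no such number can be derived and no harm is shown. The feasibility and acceptability benchmarks and their precision are unaffected.

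Confidence is high that the two wordings differ. It is lower that any site would in practice omit a test, because that depends on how sites read the protocol and on guidance not reproduced in it.

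**What to change.** In 5.4.4, replace *creatinine as needed* with *creatinine clearance at every three-monthly visit*. State the same schedule in the creatinine paragraph of 5.4.6, beside the existing action on a low result, so that both match 11.3.2. A required time window for the result before each refill would go beyond what 11.3.2 promises and is not needed to resolve the conflict.

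The cost is a wording amendment with IRB approval. The tests are already promised by 11.3.2, though they are additional relative to 5.4.4 read alone. At in-person visits, the draw can share the blood sample for HIV and syphilis testing, since 8.1 uses blood for all three. Online PrEP visits may need a separate sampling arrangement. The documents do not describe one, so the amendment should say where the sample is taken in that case.
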